7.2.5. Treatment and Disease Assessment Beyond Progressive Disease

Clinically stable subjects may continue to be treated beyond RECIST v1.1 progression at the Investigator's discretion. Subjects who receive study treatment beyond PD per RECIST v1.1 will have subsequent disease assessments evaluated using iRECIST by the Investigator.

Clinically stable subjects may continue to be treated beyond RECIST v1.1 progression at the Investigator's discretion until PD is confirmed according to iRECIST. Treatment beyond progression is permitted only in subjects who are clinically stable ([Seymour, 2017](#)). An assignment of clinical stability requires that no worsening of performance status has occurred, that no clinically relevant increases in disease-related symptoms such as pain or dyspnoea occur that are thought to be associated with disease progression, and that no requirement for intensified management of disease-related symptoms exists, including increased analgesia, radiotherapy, or other palliative care. Disease assessments should continue according to the Schedule of Assessments ([Table 1](#)).

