The confirmed iORR will be calculated as the number of subjects with a confirmed iCR or iPR divided by the number of subjects in the analysis population [iORR = (confirmed iCR + confirmed iPR)/number of subjects]. The two-sided 95% Clopper-Pearson CIs will be calculated for the iORR.

The best overall immune response (iBOR) will be derived as below:

$$\text{iCR} > \text{iPR} > \text{iSD} > \text{iCPD} > \text{iUPD} > \text{NE}$$

If assessments are not performed or cannot be assessed following iUPD, and there is no subsequent iCPD, iSD, iPR or iCR, iUPD will continue to be used and the subject will be censored at the date of iUPD.

Immune Progression-Free Survival (iPFS). iPFS is defined as the time from date of first dose of study drug to date of iCPD per iRECIST as assessed by Investigator or death, whichever occurs first. Censoring rules are detailed in [Table 1b](#).

Immune Duration of Response (iDOR). iDOR is defined as the time from the date of the first immune response (iCR or iPR) to the date of immune confirmed progressive disease (iCPD) per iRECIST by Investigator assessment.

iDOR is only defined for Subjects who have a confirmed iBOR of iCR or iPR. Subjects with a response of iCR or iPR must have a repeat tumor assessment performed no less than 4 weeks after the criteria for response are first met. The first date at which an iCR or iPR response was noted will be used to calculate iDOR, not the date of the confirmatory tumor assessment. Subjects who did not have iCPD or death will be censored at the date of their last disease assessment. Censoring rules are detailed in [Table 1b](#).

Regeneron Pharmaceuticals Inc. / Protocol: CMP-001-007
 IQVIA Biotech (Confidential) Project # SZA56629

Table 1a: Censoring Rules for the PFS/DOR

Situation	Outcome	Date	Event Description/ Censoring Reason
PD per RECIST v1.1 on/before new anticancer therapy or data cutoff date, whichever is earlier	Event	Earliest date of tumor assessment documenting PD	PD per RECIST v1.1
Death without PD per RECIST v1.1 and not receiving new anticancer therapy on/before data cutoff date	Event	Date of death	Death without PD per RECIST v1.1
[PFS only] Subjects with no post-baseline assessments	Censored	Date of First Dose of Study Drug	No Adequate Disease Assessment per RECIST v1.1

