No PD per RECIST v1.1 or Death as of data cutoff date and subject not received new anticancer therapy or received it after the data cutoff date	Censored	Date of last disease assessment on/before data cutoff date	Alive without Documented PD
No PD per RECIST v1.1 or Death as of data cutoff date and new anticancer therapy started before the data cutoff date	Censored	Date of last disease assessment prior to new anticancer therapy	Subsequent Anti-cancer Therapy without Documented PD
PD per RECIST v1.1 or Death after new anticancer therapy and the new anticancer started before data cutoff date	Censored	Date of last disease assessment prior to new anticancer therapy	Documented PD or Death after Subsequent Anti-cancer Therapy
PD per RECIST v1.1 or Death after new anticancer therapy and the new anticancer started after data cutoff date	Censored	Date of last disease assessment on/before data cutoff date	Documented PD or Death after Subsequent Anti-cancer Therapy
PD per RECIST v1.1 or Death immediately following two or more consecutive disease assessments missed since the last adequate disease assessment	Censored	Date of last adequate tumor assessment prior to missing assessments	PD or Death after Missing ≥ 2 Consecutive Disease Assessments
Withdrew consent or lost to follow-up before PD per RECIST v1.1 or Death	Censored	Date of last adequate disease assessment	Discontinued from Study without Documented PD or Death

Table 1b: Censoring Rules for the iPFS/iDOR

Situation	Outcome	Date	Event Description/ Censoring Reason
iCPD per iRECIST between scheduled disease assessments on/before new anticancer therapy or data cutoff date,	Event	Earliest date of tumor assessment documenting iUPD	iCPD per iRECIST

Regeneron Pharmaceuticals Inc. / Protocol: CMP-001-007
 IQVIA Biotech (Confidential) Project # SZA56629

whichever is earlier			
Death without iCPD per iRECIST and not receiving new anticancer therapy on/before data cutoff date	Event	Date of death	Death without iCPD per iRECIST
iPFS only iUPD per iRECIST at the time of PD per RECIST v1.1, continued study treatment without further tumor assessments as of data cutoff date	Censored	Date of the last tumor assessment on/before data cutoff date	No Adequate Disease Assessment per iRECIST

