iUPD per iRECIST, continued study treatment with subsequent disease assessments but no confirmed PD (i.e., iCPD not assigned) or Death as of data cutoff date and subject not received new anticancer therapy or received it after the data cutoff date	Censored	Date of the last tumor assessment as of data cutoff date	Alive without Documented iCPD
iUPD per iRECIST, continued study treatment, but started a new anti-cancer therapy before data cutoff date without evidence of iCPD or Death	Censored	Date of the last tumor assessment prior to new anti-cancer therapy	Subsequent Anti-cancer Therapy without Documented iCPD
iCPD per iRECIST or Death after new anticancer therapy and the new anticancer started before data cutoff date	Censored	Date of last disease assessment prior to new anticancer therapy	iCPD or Death after Subsequent Anti-cancer Therapy
iCPD per iRECIST or Death after new anticancer therapy and the new anticancer started after data cutoff date	Censored	Date of last disease assessment on/before data cutoff date	iCPD or Death after Subsequent Anti-cancer Therapy
iUPD per iRECIST, continued study treatment, iCPD or Death immediately following two or more consecutive disease assessments since the last adequate disease assessment	Censored	Date of last adequate tumor assessment prior to the first missed assessment	iCPD or Death after Missing ≥ 2 Consecutive Disease Assessments
Withdraw consent or lost to follow-up before iCPD per iRECIST or death	Censored	Date of last adequate disease assessment	Discontinued from Study without Documented iCPD or Death

Table 1c: Censoring Rules for the OS

Situation	Outcome	Date	Event Description/ Censoring Reason
Death on/before data cutoff date	Event	Date of death	Death
Alive with study completed before data cutoff date	Censored	Study completion date	Alive on or before study completion date
Alive or death after data cutoff date with study continuing on/till after data cutoff date	Censored	Data cutoff date	Alive on or before data cutoff date

Regeneron Pharmaceuticals Inc. / Protocol: CMP-001-007
 IQVIA Biotech (Confidential) Project # SZA56629

Lost to follow-up prior to data cutoff date	Censored	Last known alive date	Discontinued from study
Discontinued study without death and not lost to follow-up on/prior to data cutoff date	Censored	Date of study discontinuation	Discontinued from study

Table 2: Last Contact Date for the Overall Survival

Source Data	Conditions

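### The only row of SAP Table 1b that scores iCPD as an iPFS/iDOR event is limited to iCPD found between scheduled scans, so iCPD confirmed at a scheduled scan has no event row

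*SAP*

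**What the plan says.** SAP Section VIII.A defines the endpoints in text and refers to Table 1b for the detailed censoring rules.

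- **iPFS:** the SAP text reads "iPFS is defined as the time from date of first dose of study drug to date of iCPD per iRECIST as assessed by Investigator". An earlier death also counts as an event.
- **iDOR:** the SAP text reads "iDOR is defined as the time from the date of the first immune response (iCR or iPR) to the date of immune confirmed progressive"; that is, the interval ends at iCPD. The text censors only subjects who had neither iCPD nor death.
- **Table 1b, first row (the only iCPD event row):** "iCPD per iRECIST between scheduled disease assessments on/before new anticancer therapy or data cutoff date". The earlier of those two limits applies. The date assigned is "Earliest date of tumor assessment documenting iUPD".
- **Table 1a, parallel row for PFS/DOR:** "PD per RECIST v1.1 on/before new anticancer therapy or data cutoff date, whichever is earlier". It has no condition on scan timing.
- **Table 1b, missed-assessment row (censored), Situation cell:** "iCPD or Death immediately following two or more consecutive disease assessments since the last adequate disease assessment". Table 1a's counterpart has the word 'missed'; this cell does not.

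On timing, the SAP and protocol schedule scans at Week 10 Day 1 and every 9 weeks after that. For subjects treated beyond RECIST v1.1 progression, Protocol 7.2.5 says "Disease assessments should continue according to the Schedule of Assessments". Protocol Appendix E, which is offered as reference, calls for an earlier re-scan 4 to 8 weeks after iUPD.

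**The concern.** A censoring table exists so that the programmer does not have to decide which progressions count. Here the text says any iCPD is an event, and the table gives event status to only one kind of iCPD. The kind left out is ordinary: a subject with iUPD at one scheduled scan whose progression is confirmed at the next.

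Section I.B lets the SAP override the protocol, but nothing says whether SAP text or SAP table prevails when the two disagree. Section VIII.C plans Kaplan-Meier medians, event-free rates and tabulated censoring reasons for iPFS and iDOR. A scheduled-scan iCPD fits neither the event row nor any listed censoring reason. If such subjects were censored, people known to have progressed would be treated as still at risk of progressing, and both endpoints would look longer than they are.

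**Working it through.** The plan gives no figure on this point to reproduce. The check compares the rows, works one case, and then illustrates direction and size.

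**1. Which Table 1b row covers a scheduled-scan iCPD?** Take a subject with iUPD at W10D1 and iCPD at the scheduled W19D1 scan, with no new therapy, no missed scan and no withdrawal.

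- iCPD event row: requires iCPD between scheduled assessments. Does not apply.
- Death event row: requires death in a subject who has not had iCPD. Does not apply, even if the subject later dies.
- iUPD with no further scans (iPFS only): further scans were done. Does not apply.
- iUPD with later scans: requires that iCPD was never assigned. Does not apply.
- The three new-therapy rows: no new therapy was given. Do not apply.
- Missed-assessment row: no scan was missed. Does not apply.
- Withdrawal or loss to follow-up before iCPD or death: did not happen. Does not apply.

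No row applies. Under the text definition the subject has an event.

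**2. The same subject in months.** I assume that the SAP's PFS formula, (event or censoring date − first dose date + 1)/30.4375, also serves iPFS.

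- W10D1 is day (10 − 1) × 7 + 1 = 64, and 64/30.4375 = 2.10 months.
- W19D1 is day (19 − 1) × 7 + 1 = 127, and 127/30.4375 = 4.17 months.
- With an unrestricted event row and the table's iUPD date: event at 2.10 months.
- With no event row, and a programmer who falls back on censoring at the last scan: censored at 4.17 months.

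**3. Where would the Appendix E re-scan fall?** Four to eight weeks after day 64 is day 64 + 28 = 92 to day 64 + 56 = 120. The W19D1 scan is due on day 127 with a window of −7 days, so it may be done from day 120. The re-scan therefore normally falls between scheduled scans, where the row does apply. Both routes to confirmation exist: the Appendix E re-scan, and the regular schedule under Protocol 7.2.5. Protocol Table 1 lists a confirmatory scan for response but none for iUPD. Appendix E itself returns subjects whose iUPD is not confirmed to the regular schedule, where a later iCPD could arise.

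**4. Illustration of direction and size.** Every rate here is an assumption:

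- 24 subjects (the number treated) and 2,000 simulated trials.
- Exponential time to progression or death with median 4 months; 30% of first events are deaths.
- Scans at Week 10 and every 9 weeks; every progression is followed to iCPD.
- A between-scan iCPD is an event at the iUPD date. A scheduled-scan iCPD is censored at the confirming scan.

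| Share of iCPD at scheduled scans | Mean events | Typical median iPFS (months) | Mean 6-month iPFS |
|---|---|---|---|
| 0% | 23.7 | 4.2 | 45% |
| 25% | 19.5 | 6.2 | 53% |
| 50% | 15.4 | 8.3 | 62% |
| 75% | 11.4 | 11.4 | 70% |
| 100% | 7.1 | 23.1 | 79% |

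The 0% line is also what the unrestricted row would give at any share, because the event is dated at iUPD however it is confirmed. At 100% the median was not reached in 42.5% of the simulated trials. iDOR was not simulated; the mechanism is the same.

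**The case against.** The best defence is that this is a mismatch between text and table, not a rule to discard events. The definitions count any iCPD, and no Table 1b row censors a scheduled-scan iCPD when there is no new therapy, missed scan or withdrawal. A sensible programmer would score it as an event. That much stands: the SAP does not settle that such progressions are dropped. It does not make the row correct, because the table is where the text sends the reader for the rules.

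The defence is also right that consequences are limited. SAP Sections II.C and III make all analyses exploratory after enrolment stopped at 24. The ad-hoc analysis in Section VI.G lists ORR, DOR, TTR and PFS per RECIST v1.1, plus OS, and does not list iPFS or iDOR.

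Three stronger readings are tempting, and the documents do not support them.

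- **A reader might infer that the missed-assessment row censors iCPD after scans that were all performed**, because its Situation cell lacks 'missed'. Its Date cell refers to the first missed assessment, and its Reason cell to missing at least two in a row. With no missed scan there is no censoring date, and after adequate scans there are not two assessments since the last adequate one. This is a dropped word that the row itself supplies.
- **A reader might infer that nearly all confirmations fall on scheduled scans.** Appendix E's 4-to-8-week re-scan points the other way, and the split is unknown.
- **A reader might infer that median iPFS would drift up to overall survival.** That needs later deaths to count as iPFS events, but the death row is confined to subjects without iCPD and without new therapy, so on the same literal reading those deaths would not count.

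**Conclusion.** The point holds for the iCPD event row. As written, it leaves out an ordinary route to confirmed progression, against the SAP's own definitions and against Table 1a. If it is applied literally and the affected subjects are censored, iPFS and iDOR are biased upward.

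No single figure can be given for the size. It depends on the share of iCPD confirmed at scheduled scans and on how many of the 24 subjects are treated beyond PD. The documents give neither. The effect is nil if no iCPD is confirmed at a scheduled scan. The illustration assumes that every progression is followed to iCPD, so it exaggerates the effect in a pooled analysis where only some subjects continue past PD. It shows direction and sensitivity and does not predict the trial's result.

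The edit should be made before these analyses are run. The consequence is limited to two secondary, exploratory endpoints; the primary ORR is unaffected.

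**What to change.** In the first row of Table 1b, delete the qualifier that confines iCPD to the interval between scheduled assessments. iCPD at any assessment, scheduled or not, on or before the earlier of new anticancer therapy and data cutoff is then an event, as PD is in Table 1a.

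As an editorial repair only, insert 'missed' in the Situation cell of the missed-assessment row, to match Table 1a and that row's own Date and Reason cells.

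While the table is open, reconcile a separate mismatch: Table 1b dates the event at iUPD, whereas the text definitions run to the date of iCPD.

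The first two changes are wording edits in one SAP table and need no new data. The dating question needs a decision on which date applies, also without new data.

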- To evaluate the effect of human papillomavirus (HPV) infection and programmed death-ligand 1 (PD-L1) expressions on the efficacy of CMP-001 in combination with pembrolizumab.

C. Exploratory

- To evaluate the effect of CMP-001 in combination with pembrolizumab on injected and noninjected target lesions in subjects with HNSCC
- To evaluate the pharmacodynamic and pharmacokinetic effects of CMP-001 administered in combination with pembrolizumab

IV. Study Endpoints

A. Primary

- Objective response rate (ORR), defined as the proportion of subjects with a confirmed objective response of complete response (CR) or partial response (PR) based on Response Evaluation Criteria in Solid Tumors version 1.1 (RECIST v1.1) as determined by Investigator assessment.

B. Secondary

- Adverse events (AEs), serious adverse events (SAEs), and AEs leading to discontinuation or death, and severity of AEs as assessed by the National Cancer Institute Common Terminology Criteria for Adverse Events (NCI CTCAE), version 5.0.
- Duration of response (DOR), defined as the time from date of first

Regeneron Pharmaceuticals Inc. / Protocol: CMP-001-007
IQVIA Biotech (Confidential) Project # SZA56629

documented response (CR or PR) to date of documented progressive disease (PD), based on RECIST v1.1 by Investigator assessment.

- Progression-free survival (PFS), defined as the time from date of first dose of study drug to date of documented PD based on RECIST v1.1 by Investigator assessment or death, whichever occurs first.
- Overall survival (OS), defined as the time from the date of first dose of study drug to the date of death.
- Immune objective response rate (iORR), defined as the proportion of subjects with a best overall response (BOR) of immune complete response (iCR) or immune partial response (iPR) based on the immunotherapy Response Evaluation Criteria in Solid Tumors (iRECIST) by Investigator assessment.
- Immune duration of response (iDOR), defined as the time from the date of the first immune response (iCR or iPR) to the date of immune confirmed progressive disease (iCPD) by Investigator assessment.
- Immune progression-free survival (iPFS), defined as the time from date of first dose of study drug to date of iCPD by Investigator assessment or death, whichever occurs first.
- ORR, DOR, and PFS based on HPV status and PD-L1 expressions (combined positive score [CPS] ≥ 1 and CPS ≥ 20).

C. Exploratory

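### The SAP gives two different event dates for iPFS and iDOR, and the one in Table 1b can fall before the response it is meant to end

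*SAP*

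**What the plan says.** SAP IV.B lists iPFS as a secondary endpoint, "defined as the time from date of first dose of study drug to date of iCPD by Investigator assessment or death". SAP VIII.A repeats this: "iPFS is defined as the time from date of first dose of study drug to date of iCPD per iRECIST". For iDOR, VIII.A sets the start with "The first date at which an iCR or iPR response was noted will be used to calculate iDOR", and the end runs "to the date of immune confirmed progressive disease (iCPD) per iRECIST by Investigator assessment". The Protocol (Synopsis and Section 2.2.2) uses the same iCPD end dates.

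For censoring and event rules on both endpoints, VIII.A refers to Table 1b. The only row there that counts iCPD as an event opens with "iCPD per iRECIST between scheduled disease assessments" and gives as its date "Earliest date of tumor assessment documenting iUPD".

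Two further statements bear on death after an unconfirmed progression. After the iBOR ranking, VIII.A says of a subject with no usable assessment after iUPD that "iUPD will continue to be used and the subject will be censored at the date of iUPD". Table 1b counts as an event "Death without iCPD per iRECIST and not receiving new anticancer therapy on/before data cutoff date".

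Protocol Appendix E treats iUPD as reversible. A later scan may give iSD, iPR or iCR, and an iUPD does not override a later best response of that kind. If the lesions are unchanged, iUPD status is kept, so several iUPD scans may precede iCPD.

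**The concern.** The definitions and the table they cite give different dates for the same event. SAP I.B says that the SAP governs over the protocol, but that does not help when the SAP disagrees with itself.

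Table 1a uses the same pattern for RECIST v1.1: the earliest scan documenting PD. That is safe where the first PD is the event. It is not safe for iUPD, which can be overturned. The Table 1b row does not say that the iUPD must belong to the episode that ended in iCPD, or that it must follow the response. Because VIII.A ranks iCR and iPR above iUPD in iBOR, a confirmed responder with an earlier, overturned iUPD is in the iDOR set. Read as written, that subject's response can end before it begins, and the subject's iPFS is cut back to the overturned scan.

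Both endpoints are secondary, with Kaplan-Meier medians and event-free rates planned in VIII.C. Two programmers working from this text could derive different dates.

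**Working it through.** The documents give no iPFS or iDOR figure to reproduce, so the check applies the stated rules to constructed timelines.

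**Inputs**
- Scans at Week 10 Day 1, then every 9 weeks (SAP VIII).
- Re-evaluation of iUPD after 4 to 8 weeks (Protocol Appendix E).
- Months = (end date - start date + 1) / 30.4375. SAP VIII.A gives this for PFS and DOR. It gives no formula for iPFS or iDOR, so using it here is an assumption.
- Study day of Week k Day 1 = 7(k - 1) + 1. Hence W10 = 64, W19 = 127, W27 = 183, W55 = 379, W59 = 407.

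**1. One ordinary episode, no reversal.** The gap between the two stated dates is the time from iUPD to iCPD.
- Confirmation after 4 weeks: 28 / 30.4375 = 0.92 months
- After 8 weeks: 56 / 30.4375 = 1.84 months
- At the next 9-week scan: 63 / 30.4375 = 2.07 months

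**2. An overturned iUPD followed by a response.** Take iUPD at W10, iPR at W19 (confirmed at W28), a new iUPD at W55, and iCPD at W59. W59 is an unscheduled 4-week re-evaluation between the W55 and W64 scans, so the event row reaches it even with its scheduling qualifier.

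| Event date used | Day | iDOR = (day - 127 + 1) / 30.4375 | iPFS = (day - 1 + 1) / 30.4375 |
|---|---|---|---|
| Earliest iUPD (Table 1b as written) | 64 | -62 days = -2.04 months | 64 days = 2.10 months |
| iUPD of the confirmed episode | 379 | 253 days = 8.31 months | 379 days = 12.45 months |
| iCPD (IV.B and VIII.A) | 407 | 281 days = 9.23 months | 407 days = 13.37 months |

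Table 1b also behaves oddly as follow-up grows. If the data cutoff falls just after W55 with treatment continuing, its row for iUPD without later confirmation censors iPFS at the last scan, 12.45 months. One more scan showing iCPD turns that into an event at 2.10 months.

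With 24 subjects and no earlier censoring, one such subject moves the 6-month iPFS rate by 1/24 = 4.2 percentage points, because only the Table 1b date falls before 6 months.

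**3. Several iUPD scans before iCPD.** With iUPD at W10 and again, unchanged, at W19, followed by iCPD, iPFS is 64 / 30.4375 = 2.10 months from the first iUPD and 127 / 30.4375 = 4.17 months from the last. A rule based on iUPD therefore has to say which one.

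**4. Death with no scan after iUPD (minor).** Take iUPD at W10, the W19 scan missed, and death at W27 without new therapy. The iUPD sentence in VIII.A censors at 64 / 30.4375 = 2.10 months. So does the iPFS-only row in Table 1b if treatment continued. The death row gives an event at 183 / 30.4375 = 6.01 months. No order is stated. The tie-break in the PFS paragraph names only PFS and ranks only censoring rules.

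**The case against.** The best defence is that iCPD is by definition the confirmation of a preceding iUPD, so the natural reading is the first scan of the progression being confirmed. On that reading the word earliest simply picks the first of several consecutive iUPD scans, and no careful programmer would accept an end date before the response. This is a sensible reading and may well be the intent. But the SAP does not state it, and it leaves the definitions still pointing at iCPD, 0.9 to 2.1 months later. Appendix E defers to the original iRECIST publication for discrepancies; that source may settle the reset, but it cannot be consulted here.

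Several stronger inferences should be resisted:
- **That dating back to iUPD is itself an error.** It is a legitimate convention, and Appendix E uses it for a new lesion that is later confirmed. The fault is the disagreement and the missing anchor.
- **That iCPD found at a scheduled scan would not count.** The row's qualifier leaves that case without an explicit row, but the VIII.A definitions make any iCPD the end point. This looks like stray table wording, although it does mean that an example with iCPD at a scheduled scan would not test the row as written.
- **That deaths after iUPD are generally lost.** VIII.A makes death an iPFS event and implies that a death is not censored for iDOR. The conflict is confined to subjects never rescanned who die without new therapy and outside the missed-assessments row. If the 4-to-8-week re-evaluation counts as an assessment, it is narrower still.
- **That the trial's iPFS or iDOR results are wrong.** The documents do not say whether any subject had the sequence that triggers the problem.

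**Conclusion.** Wrong as written. The SAP states two event dates for the same iCPD event, and the Table 1b date is not limited to the confirmed episode. In an ordinary case the dates differ by 0.9 to 2.1 months. In the illustrated reversal, iDOR is -2.0, 8.3 or 9.2 months and iPFS is 2.1, 12.5 or 13.4 months, depending on which date is used.

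These figures assume that the PFS/DOR month formula carries over and that scans fall on schedule. The large discrepancy needs iUPD, then iSD, iPR or iCR, then a later iCPD. The impossible order (event before response) concerns iDOR only; iPFS is shortened but cannot become negative. Consequences are bounded: after early termination of enrollment all analyses are descriptive and exploratory (SAP II.C), the number of affected subjects among the 24 may be zero, and the primary ORR does not use these dates. It should still be corrected, because both are named secondary endpoints and the derivation cannot be programmed unambiguously.

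**What to change.** State one event date, in the same words, in SAP IV.B, SAP VIII.A and Table 1b. Either choice can work:
- **Keep iCPD** as in the current definitions, and change the date cell in Table 1b to match.
- **Keep iUPD dating**, defined as the first iUPD of the run that ends in iCPD, with the run reset by any intervening iSD, iPR or iCR. Say how a not-evaluable or missed scan inside the run is treated. Note that this departs from the iCPD end date in the Protocol Synopsis and Section 2.2.2, with the SAP governing under I.B.

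Remove the scheduling qualifier from the iCPD event row so that it covers every iCPD.

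As a minor addition, state that the Table 1b death row takes precedence over the iUPD-censoring sentence in VIII.A and over the iPFS-only row when a never-rescanned subject dies without new therapy and the missed-assessments row does not apply. That agrees with the iPFS definition, which already counts death.

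The cost is SAP wording, a few Table 1b cells and the matching derivation code. No new data or additional output is needed. Estimates may move in either direction.
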